$$Y_{ijkm} = A_{ikm} + B_i X_{jkm} + C E_{ijkm} + D_i E_{ijkm} X_{jkm} + L_i(t) Y_{i[j-1]km} + F Z_k + D S_m + Q q_{jmk} + \mu_{imw} + \nu_{it} \quad ; \quad i=1, \dots, 6 \quad (2)$$

We will then test the hypothesis as above by calculating the $PP[\text{Abs}(D_i) > 0, i=1, \dots, 6]$

In the event that the model with patient surveys as the unit of analysis cannot be computed to test Hypotheses H1b, we will use the cluster-period approach outlined for testing H1a, but will summarize SPPADE NRS scores for each cluster-period according to whether the patient had any prior elevated scores; we will then estimate a model analogous to the cluster-period model used to test Hypothesis H1a but including an indicator for post-elevation and the interaction with the intervention indicator.

Finally, as a secondary objective of this aim, to better understand the effectiveness of different components of the E2C2 intervention in reducing symptoms, we will perform a separate set of analyses to assess the impact of specific process measures (D.2.d) on SPPADE scores and other clinical outcomes. For each process measure we will first examine the distribution of values (frequency or duration) and, if highly skewed, categorize into 2 or more categories. We will then estimate for each outcome a mixed effects linear model with a random cluster effect, where the outcome is the dependent variable and the main independent variable is the continuous or categorized process measure, adjusting for patient covariates as described above. By testing for an overall process measure effect, we can assess which processes contribute most to reducing outcomes; we will also report measures of variance explained to enable relative comparison of process measure effects.

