Specific Aim 2 Analyses. We will summarize patient characteristics (sex, age, insurance status) by intervention status (baseline, intervention). We will also summarize all survey responses by cluster implementation status, including clinician characteristics (age, sex, years of practice). All patients will be analyzed on an intention to treat status; this principle will be extended to the cluster status, so that delays in implementation of an intervention will not affect the intervention status of patients.¹⁰¹ All methods will account for correlation of outcomes within clusters and across patients. As a secondary objective of this aim, we will assess the change in clinician survey constructs over time. This analysis will include each clinician with at least two completed surveys at least 6 months apart.

As in Aim 1, we will also assess the effect of process measures on SPPADE scores and other clinical outcomes. We will use models appropriate for count data, selecting standard or zero-inflated Poisson or negative binomial models according to Aikake's Information Criteria, or logit models for binary measures. For each outcome we will estimate a) bivariate models including only one survey score; b) a model with all scores; and c) a final model which also includes clinician characteristics.

Aim 3

Endpoints

Primary:

SPPADE and physical function NRSs will serve as both the E2C2 primary outcome and a critical component of the E2C2 intervention since NRS scores populate the EHR algorithms that determine whether patients are triaged to Level 1 or 2,

and whether patients are offered specific intervention components (education, medications, etc.). Patients will complete NRSs for SPPADE symptoms and physical function prior to medical oncology clinic appointments at all stages of the trial, i.e., prior to and after E2C2 initiation. ePROs will be more frequently administered to symptomatic patients outside of their appointment-linked assessments as part of the intervention. *To avoid potential bias from oversampling of symptomatic patients, only SPPADE symptom NRSs collected in association with clinic appointments will be included in the primary analysis.*

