Health care utilization. Healthcare utilization for E2C2 will consider health care encounters including hospitalizations, ED visits, ICU admissions, clinic outpatient visits, and calls to the oncology care team. EHR entries and administrative billing data will be aggregated to construct a comprehensive data set of all clinical encounters. Data collected for hospitalizations will include admission and discharge diagnoses, length of stay, ICU admission/transfer, and whether an admission was planned for anti-cancer treatment or unplanned, and if the latter, initiated from the ED or an office visit. For ED encounters, we will capture diagnoses and whether an encounter resulted in hospital or ICU admission. Clinic visits will be captured using billing data which will include CPT codes, ICD-10 codes, location, and clinician NPI numbers. We will be able to ascertain clinician discipline and specialty from the NPI numbers. Calls to the oncology care team are not billed but are reliably captured in the EHR. A recent audit established that 87% of calls to medical oncology practitioners were recorded in the EHR, and that rates of capture did not vary systematically across disciplines. However, call characteristics, e.g., duration, were not reliably recorded. Therefore we will use count data in analyses to model call frequency.

We will estimate mixed effects Poisson regression models with utilization events during the trial period as dependent variables. Because utilization events will be available for all trial participants, we will perform analyses with cohorts comprised of all trial participants and those who completed ≥ 1 ePROM, and ≥ 2 ePROMs.

The majority, but not all, of patients' health care utilization will occur at MC facilities. Established patterns suggest that 75% to 80% of patients care will occur at an MC facility and that this frequency will not vary across E2C2 clusters, or phases of the E2C2 intervention, e.g., pre-E2C2, Stage 1. However, we will perform analyses that include only patients residing within driving distance of a trial site to assess the impact of distance. Additionally, we will use imputation methods and sensitivity analyses to assess the impact of mis-ascertainment of utilization data.

Cancer treatment adherence. The literature does not offer a definitive definition of cancer treatment adherence, even

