for medications, or clarify which of the many candidate measures should be considered.¹²¹ We will therefore assess adherence broadly and examine the frequency of missed imaging, medical oncology clinic visits, and chemotherapy appointments. Additionally, we will capture any unplanned hiatuses in cancer treatment or dose reductions. This information is routinely recorded on electronic chemotherapy administration forms from which discrete structured data elements can be abstracted. For oral hormonal regimens we will use the accepted definition of at least 80% of recommended doses to create a binary variable.¹²² [name] (E2C2 Co-I) has contributed seminally to the literature on adherence to breast cancer adjuvant therapies.^{123,124} We will apply this criterion to oral chemotherapy and immunotherapy as well.

Vital status. Vital status will be verified through death certificates, the Mayo Clinic EMR, next-of-kin reports, the Mayo Clinic Tumor Registry and the Social Security Death Index website.

Reporting mode and rates. Patient reported outcomes will be collected via several modes for the E2C2 trial. These include remote modes; the patient portal and interactive voice response, and point of care modes; tablets and provider entry via Epic Care. Data regarding patients' mode of PRO reporting are automatically stored by the Epic EHR. We will perform descriptive statistics to characterize how reporting modes differ across subgroups defined by demographic, clinical, cancer-related, and symptom characteristics. Additionally, we will create uni- and multi-variate mixed models to estimate associations of reporting frequency and mode with patient characteristics.

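### The Aim 1 process-measure analysis gives one linear mixed model for every outcome, with no follow-up term; for utilization counts this conflicts with the plan's own Poisson model.

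*Combined protocol and SAP*

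**What the plan says.** The last paragraph of the Specific Aim 1 analyses, after the H1b model, sets a secondary objective: to "assess the impact of specific process measures (D.2.d) on SPPADE scores and other clinical outcomes". The other clinical outcomes are not listed there, and the section cited as D.2.d is not in the document. One model is then given: "We will then estimate for each outcome a mixed effects linear model with a random cluster effect". The process measure is the main predictor, and the patient covariates described earlier are adjusted for. The rule on skewness concerns the predictor only: "For each process measure we will first examine the distribution of values (frequency or duration) and, if highly skewed, categorize into 2 or more categories". Components are to be compared on one metric: "we will also report measures of variance explained to enable relative comparison of process measure effects".

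Three other places bear on this.

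- Endpoints, Health care utilization: "We will estimate mixed effects Poisson regression models with utilization events during the trial period as dependent variables". Calls to the care team are also to be analysed as counts.
- Specific Aim 2 Analyses: "As in Aim 1, we will also assess the effect of process measures on SPPADE scores and other clinical outcomes", followed by "We will use models appropriate for count data, selecting standard or zero-inflated Poisson or negative binomial models", with the choice made by AIC, and logit models for binary measures.
- Endpoints, Cancer treatment adherence: for oral regimens the plan takes "at least 80% of recommended doses to create a binary variable". Missed imaging, clinic visits and chemotherapy appointments are recorded as frequencies.

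Vital status has a paragraph on how it is verified. No survival model is given anywhere.

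**The concern.** Aim 1 itself names unplanned hospitalizations, ED visits, ICU admissions and treatment adherence, and the Overall Study Design section adds survival. An objective of that aim that covers other clinical outcomes would ordinarily include these. They are counts, a binary variable, missed-appointment frequencies and a censored time. A linear model is reasonable for the NRS and PROMIS scores. For the rest it raises three questions.

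- **Which model governs?** An analyst with utilization counts finds a linear model in one section and Poisson in another.
- **Are the intervals right?** The linear model assumes one error variance, but the variance of a count rises with its mean.
- **Is time under observation handled?** The covariates listed for Aim 1 (cancer type and stage, age, sex, Elixhauser score, area education, income and broadband) do not include it. Enrolment is population-based over 46 or 47 months (a first period given as 6 months in Figure 1 and 7 in the text, plus 5 × 8), so follow-up will probably vary widely.

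The analysis is meant to show which components of E2C2 do most, so it bears on which are kept. A component could look harmful or protective when it is neither.

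**Working it through.** The plan gives no sample size, power or error rate for this analysis, so there is no stated figure to reproduce. It also gives no event rates, follow-up lengths or prevalence of process use. All inputs below are assumptions.

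**1. The sections side by side**

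| Outcome type | Aim 1 process analysis | Elsewhere in the plan |
|---|---|---|
| NRS, PROMIS scores | linear | linear for NRS: no conflict |
| Utilization counts | linear | mixed Poisson (Endpoints); count models (Aim 2) |
| Oral-therapy adherence, yes/no | linear | logit (Aim 2) |
| Survival, if included | linear | none: a gap, not a conflict |

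**2. Interval coverage**

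Take a yes/no process measure with share f exposed, and outcome variances v1 (exposed) and v0 (unexposed). Within a cluster, the linear model's variance for the mean difference divided by the true variance is

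R = [f·v1 + (1−f)·v0] / [(1−f)·v1 + f·v0], and coverage = 2Φ(1.96·√R) − 1.

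For Poisson counts the variance equals the mean. With f = 0.10:

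| Mean exposed / unexposed | R | Coverage |
|---|---|---|
| 0.8 / 0.2 | (0.08+0.18)/(0.72+0.02) = 0.351 | 75% |
| 0.4 / 0.2 | (0.04+0.18)/(0.36+0.02) = 0.579 | 86% |
| 0.2 / 0.2 | 1 | 95% |
| 0.1 / 0.2 | (0.01+0.18)/(0.09+0.02) = 1.727 | 99% |

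At f = 0.50, R = 1 and coverage is 95% whatever the effect.

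A wider grid took f = 0.05 and 0.20, unexposed means 0.3 and 1.0, and variance m + k·m² with k = 0 or 1. Coverage was 77% to 89% for a rate ratio of 2.0, 86% to 92% for 1.5, 96% to 98% for 0.8, and 98% to 99.8% for 0.5. For binary adherence of 90% in the unexposed, and 5 or 10 points lower in the exposed, coverage was 87% to 92%.

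**3. Shared follow-up time**

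Let a patient be observed for time t, with contacts x ~ Poisson(a·t) and events y ~ Poisson(b·t), independent given t, so that there is no true relation. Then Cov(x, y) = a·b·Var(t), and the linear slope of y on x is

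b·Var(t) / [E(t) + a·Var(t)],

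which is above zero whenever follow-up varies. Take t uniform on 1 to 40 months, a = 0.10 and b = 0.03 per month. Then E(t) = 20.5 and Var(t) = 39²/12 = 126.75.

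- Slope = 3.80/(20.5 + 12.68) = 0.115 events per contact.
- R² = 0.380²/(3.318 × 0.729) = 0.060.
- With 1,500 patients, the test statistic is about √(1500 × 0.060/0.940) = 9.8.

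In simulation of this setting the linear model rejected the true null in 100% of 300 runs.

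A second setting separates the causes. It has 3,000 patients, entry spread over 47 months, median survival 3 years, and 0.5 admissions and 1 contact per person-year, independent of each other.

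| Model of admissions on contacts | False rejection |
|---|---|
| Linear, cumulative contacts | 100% (+0.22 admissions per contact, R² 12%) |
| Poisson, cumulative contacts, no offset | 100% |
| Linear, contacts in first 6 months only | 4% |
| Poisson with offset, contacts in first 6 months only | 5% |
| Poisson with offset, contacts as a rate | 4% |

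The cause is the missing follow-up time, not the linear form. A linear model of death on cumulative contacts in the same setting also rejected in 100% of runs, with a slope of about −0.047 per contact: those who live longer collect more contacts.

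**4. Ranking of components**

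Two process measures were ranked by linear variance explained and by deviance from the matching count or logit model (15 clusters, 1,500 patients, 200 runs per scenario). The rankings disagreed in 0% to 4% of runs in seven of eight scenarios. They disagreed in 21% in the eighth, a count outcome with 10% exposed to each measure and effects of opposite sign.

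**5. Survival, if included**

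With exponential survival of mean 24 months, hazard ratio 0.7 and censoring uniform on 1 to 40 months, the true difference in means is 24/0.7 − 24 = 10.3 months. Mean observed time is m − (m²/39)(e^(−1/m) − e^(−40/m)). That is 12.6 months for m = 24 and 14.4 for m = 34.3, so a linear model on observed time would show 1.8 months.

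**The case against.** The strongest reply has five parts.

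- **Scope is inferred.** The paragraph names no count, adherence or survival outcome, and its stated purpose is to understand symptom reduction. This is fair, but its own wording goes beyond SPPADE scores, and Aim 1 lists utilization and adherence. The inference is strong though not certain.
- **Aim 2 may ask a different question.** Its predictors are survey scores and clinician characteristics, so process measures may be the dependent variables there. If so, there is no conflict with Aim 2, but the conflict with the utilization section remains. If it is the same question, suitable families are already in the plan and only need to be referred to.
- **Process measures may not be per-patient counts.** The Overall Study Design and Audit and Feedback sections describe stakeholders' and clinicians' use of EHR tools. Measures defined per clinician, or outcomes counted over fixed intervals, would shrink the follow-up problem. However, the section on nurse-facilitated collaborative care records the frequency and duration of calls in order to study them as mediators, and a cumulative count is the simplest way to use those data.
- **A linear model for a mean or risk difference is defensible.** Coverage is nominal under no effect or with half exposed, and intervals are too wide, not too narrow, when a process reduces events. Robust standard errors would deal with unequal variance. This stands, but the plan does not mention them.
- **The plan's Poisson models state no offset either.** This is correct, so changing the family alone would not cure the false association.

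A reader might infer from the 100% figures that the linear form itself creates false positives. It does not: with contacts from a fixed early window the linear model rejected in 4% of runs.

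**Conclusion.** The concern holds in a limited form. The plan states a linear model for every outcome of the process-measure analysis, with no follow-up term. For utilization counts this contradicts the utilization section, and probably Aim 2.

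Its size rests on assumed inputs. With 10% exposed, coverage of a nominal 95% interval runs from about 75% (event mean four times higher in the exposed) to 99% (event mean halved). A near-certain false association arises only if the process measure is a cumulative count per patient and follow-up is unequal and not modelled; it would arise with Poisson too.

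Two stronger readings are not supported. The first is that the ranking of components is wrong: in seven of eight scenarios the linear and generalized rankings disagreed in at most 4% of runs. The second is that the plan contradicts itself on survival: it gives no survival model and does not say that survival enters this analysis.

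The analysis is secondary and does not compare randomized groups. H1a and H1b are untouched. It should still be settled before analysis, because the result may guide which components are kept.

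**What to change.** In the process-measure paragraph of Aim 1:

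1. List the outcomes and define each process measure, including its unit (patient or clinician).
2. Limit the linear mixed model to the NRS and PROMIS scores.
3. For utilization and missed-appointment frequencies, use the count mixed models already named under Aim 2 and Health care utilization, with a log person-time offset.
4. Use a logit mixed model only for the binary 80% oral-therapy measure.
5. If survival is included, use a time-to-event model with the process measure time-updated or taken at a landmark.
6. Express cumulative per-patient process measures per unit of observed time or over a fixed early window.
7. For the non-linear models, replace variance explained by deviance explained, and compare components only within one outcome.

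Add the person-time offset to the count models under Aim 2 and Health care utilization as well, and say in Aim 2 whether process measures are predictors or outcomes.

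The cost is a short SAP revision and somewhat more analysis work. No new data are needed. The one loss is a single variance-explained metric across all outcomes.

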We will summarize patient-, cluster-, and survey-level characteristics (e.g., sex, age, cancer type and stage, insurance status) by intervention status (pre-E2C2, E2C2) of the encounter. All analyses will be conducted on an intention to treat basis. The primary analysis will test differences in change in joint SPPADE symptom NRS scores in all participants, and in those who report elevated (4-10/10) symptoms, between participants who are exposed to the intervention and those who are not. We have two primary hypotheses. The first will assess the effect of the intervention across the full cohort of patients enrolled, Hypothesis *H1a*. The second will assess the effect of the intervention among patients who report moderate or worse symptoms, Hypothesis *H1b*. The rationale for Hypothesis *H1b* is that some intervention components are only offered to participants who report elevated symptom scores. Additionally, a large proportion of the trial cohort will only report mild or no symptoms. Among these participants there is little or no opportunity to improve symptoms and no practical exposure to the intervention. The original hypotheses regarding population-level effects will retain primary importance, yet it is critical to test intervention effects in the subset of patients that ever have elevated symptom scores.

We will include a common set of variables in all models testing the effectiveness of the intervention. Cancer type and stage will be included, as well as 7 variables selected as likely to impact the use of the portal and completion of the

[figure not shown]

Figure 3. Power simulations for E2C2 Interventions

surveys: from the EHR we will capture age (categorized into 10-year increments), sex (male or female), and severity of illness (Elixhauser score as a categorical variable). We will also link the patient 9-digit zip code to Census data to get estimates of educational level, income, and broadband access, which will be categorized into quartiles.

Hypotheses H1a

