In the event that the model with patient surveys as the unit of analysis cannot be computed, we will use an alternative cluster-period model for the primary analysis. We will aggregate outcomes and covariates for each cluster for each time period and use these cluster-level estimates to assess the effect of the intervention. We will calculate the mean of each of the 6 different SPPADE NRS scores collected during trial cluster-periods. We will also calculate the mean baseline score for each participant that reports one or more ePROMs. We will then test the first primary hypothesis using a multivariate regression model using these 15 clusters \times 6 period = 90 cluster-period values, including an indicator for intervention status for each cluster-period, and adjusting for mean baseline scores and including indicators for study step to account for secular trends and for indicators for cluster to account for cancer type. We will adjust for cluster-period averaged values of factors of patients reporting during each period for which the SMD between intervention and control cluster-periods are >0.2 .

To assess the robustness of using the CP model, we will replicate the main analyses for each symptom NRS score. We will use the originally specified generalized mixed effects model, as well as the CP model adapted to the univariate dependent variable. This former model will be estimated at the survey level, with random effects for surveys within patients and patients within clusters; these 6 models (one for each symptom score) also included all pre-specified patient covariates, baseline symptom score, the lag in weeks since the baseline measurement and the interaction of the lag time with the baseline effect.

Because there is potential for the intervention to impact the baseline scores as well, we will replicate the cluster-period and survey level models each symptom score, including patients with only 1 survey score.

We will estimate models using the STAN software package.

Hypotheses H1b

To test whether the intervention has a differential effect on those patients with at least one elevated symptom score,

we will construct an indicator, E_{ijkm} , varying by measurement time, which indicates whether the i^{th} prior symptom score was elevated (>3). By interacting these indicators with the main intervention effects B_i we can assess the impact of the intervention on the corresponding scores of patients with at least one elevated score:

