Receptivity to receipt of symptom support. The E2C2 intervention provides low and high touch support for moderate and severe symptoms, respectively. Patients who endorse moderate symptoms (4-6/10) are offered the option to receive symptom self-management education materials for specific symptoms, Sleep disturbance, Pain, Anxiety, Depression, Fatigue, and Deficits in physical function. Similarly, patients who endorse severe symptoms (7-10/10) are offered the opportunity to discuss the same symptoms with a nurse symptom care manager. We will calculate descriptive statistics to characterize patients' preferences with regard to receipt of symptom support in subgroups defined by symptom type and intensity, as well as the stability of their preferences for symptom support. Additionally, we will estimate associations between patients' demographic and clinical characteristics and their interest in receiving support by constructing multivariate mixed models.

BIBLIOGRAPHY AND REFERENCES CITED

1. [name] AL, Shen T, Chang M, Basford JR. Appropriateness of the treatment of fatigued patients with stage IV cancer. *Support Care Cancer* 2013;21(1):229-33. DOI: 10.1007/s00520-012-1515-7.

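### The secondary process-measure models omit the prior score, calendar time and patient effects, so the planned ranking of intervention components would be distorted by triage and secular drift

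*Combined protocol and SAP*

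**What the plan says.** The last paragraph of the Specific Aim 1 analyses (Data Analysis Plan, after the H1b model) sets out a separate group of analyses of process measures. Each outcome gets "a mixed effects linear model with a random cluster effect", with the continuous or categorised process measure as main predictor, "adjusting for patient covariates as described above". The stated use is: "By testing for an overall process measure effect, we can assess which processes contribute most to reducing outcomes". Variance explained will also be reported so that measures can be compared.

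The covariates referred to are those at the start of the Aim 1 analyses: "Cancer type and stage will be included, as well as 7 variables selected as likely to impact the use of the portal" and the completion of surveys. Those then named are age, sex, Elixhauser score and Census-based education, income and broadband access. None is a prior score or a time term. Under H1a, the survey-level robustness models "also included all pre-specified patient covariates, baseline symptom score", so the plan itself treats the baseline score as separate from the patient covariates.

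Model (1) under H1a, for the same SPPADE scores, has the lagged score with a time-dependent coefficient, calendar quarter, patient and cluster random effects, cluster-by-step effects and an AR(1) process.

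The scores also drive delivery. The Endpoints section says that NRS scores feed the algorithms that assign Level 1 or 2 and offer components. Under Receptivity to receipt of symptom support, "patients who endorse severe symptoms (7-10/10) are offered the opportunity to discuss the same symptoms with a nurse symptom care manager".

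Specific Aim 2 Analyses returns to the topic: "As in Aim 1, we will also assess the effect of process measures on SPPADE scores and other clinical outcomes". It then names Poisson, negative binomial and logit models.

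**The concern.** The analysis is meant to say which components deserve credit, and a reader could use it to decide what to keep. Three features work against that.

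- **Triage.** A high score leads to the offer of nurse contact or education, and high scores tend to persist. Without the prior score, the coefficient mixes any effect of the component with the reason for offering it.
- **Time.** The Symptom Control Bundle is activated at go-live, and the Implementation Bundle and the clinician dashboard start with it. Process use is therefore zero before crossover and more common in later steps. Without a time term, the measure can stand in for calendar time.
- **Repeated scores.** Questionnaires can be assigned as often as every two weeks, so patients can contribute several scores. A cluster effect alone treats scores from one patient as independent given the cluster.

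Variance explained ignores sign, so a strong triage artefact would rank high on that scale.

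**Working it through.** **Plan's own figure.** None is given for these models. The only power statement (70% at a difference of 0.10, nearly 100% at 0.20) concerns the primary model. Everything below rests on assumed values.

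**1. Interval width.** For survey-level scores and a process measure constant within patient, with m scores per patient and within-patient correlation ρ:

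- DEFF = 1 + (m − 1)ρ
- true SE / model SE = √DEFF
- actual size of a nominal 5% test = 2[1 − Φ(1.96/√DEFF)]

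If the measure varies within patient, with exposure correlation ρx, DEFF is about 1 + (m − 1)ρρx.

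| m | ρ | DEFF, constant measure | SE too small by | Actual size | DEFF, ρx = 0.3 | Actual size |
|---|---|---|---|---|---|---|
| 3 | 0.3 | 1 + 2×0.3 = 1.60 | 21% | 12.1% | 1.18 | 7.1% |
| 5 | 0.5 | 1 + 4×0.5 = 3.00 | 42% | 25.8% | 1.60 | 12.1% |
| 8 | 0.7 | 1 + 7×0.7 = 5.90 | 59% | 42.0% | 2.47 | 21.2% |

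A null simulation with 15 clusters of 60 patients, scores limited to 0–10 and a measure constant within patient agrees: for m = 2 to 6 and ρ = 0.3 to 0.7, rejection was 8% to 34%.

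**2. Triage, true effect zero.** Assumptions: same 15 × 60 layout, four outcome scores per patient, mean 3, SD 2.5, cluster SD 0.4, and a call after half of the prior scores of 7 or more. A within-cluster estimator stands in for the cluster random effect; 200 runs per row.

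| ρ | Coefficient, no prior score | Rejects | Variance explained | Coefficient, prior score added | Rejects |
|---|---|---|---|---|---|
| 0.3 | +1.30 | 100% | 1.4% | −0.015 | 11% |
| 0.5 | +2.21 | 100% | 3.8% | 0.001 | 8% |
| 0.7 | +3.11 | 100% | 7.5% | −0.020 | 9.5% |

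The prior score removes the bias here because it is the only trigger simulated. The remaining excess over 5% is consistent with the patient effect still being absent.

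**3. Time, true effect zero.** Assumptions: the Figure 1 schedule, 100 independent scores per cluster-period, SD 2.5, no process use before crossover and Poisson use with mean 1 after it; 300 runs per row.

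| Drift per step | Coefficient, no time term | Rejects | Coefficient, step terms added | Rejects |
|---|---|---|---|---|
| −0.02 | −0.017 | 9% | 0.000 | 6% |
| −0.05 | −0.044 | 31% | 0.000 | 6% |
| −0.10 | −0.084 | 76% | 0.002 | 5% |

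Triage pushes towards apparent harm and an improving trend towards apparent benefit. The ranking error therefore has no fixed direction across measures.

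**The case against.** **The plan makes general commitments.** The overview of study design promises methods suited to stepped-wedge cluster trials. The H1a section says that models will account for correlation within clusters and across patients and adjusts for study period. Aim 2 repeats the correlation statement. This stands in part: the plan conflicts with itself and cannot simply be said to ignore correlation. But the process-measure paragraph gives an explicit, separate specification. None of these sentences adds a prior score to it or names a time term for it.

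**The unit of analysis is not stated.** This stands. With one record per patient, the within-patient inflation disappears. For measures that vary over time it shrinks, as the table shows.

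**The list of process measures (D.2.d) is not in the supplied text.** This stands. Measures described elsewhere include clinician actions such as dashboard use and responses to advisories. For those, score-driven triage matters less, and the time term and clinician-level clustering matter more. Nurse contact is described as a possible mediator in the care-manager section, so its inclusion here is plausible but not shown.

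**Stronger readings that the documents do not support:**

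- A reader might infer that nurse contact could look helpful through regression to the mean. That does not follow from a model of score levels without a prior score; the triage simulation showed only apparent harm.
- A reader might infer that the plan will declare many processes significant by chance. That would need figures for survey counts, correlations and persistence of exposure, which the plan does not give.
- A reader might infer that Aim 2 applies count models to SPPADE scores. The paragraph can also be read with utilisation counts or process counts as outcomes, so it is unclear drafting and not a demonstrated error.

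**Conclusion.** The concern holds for the specification as written. The models lack the prior score, time terms and patient effects that model (1) uses for the same scores, and their coefficients are then read as showing that "we can assess which processes contribute most to reducing outcomes". For score-triggered, patient-level measures, bias towards apparent harm follows from the triage rules. Its size (1.3 to 3.1 points) rests on the assumed mean, SD, correlation and call rate. For any measure, drift can be mistaken for effect; the size depends on a drift that the plan does not quantify. The test size of about 12% to 42% applies only to survey-level outcomes and measures constant within patient, under the assumed counts and correlations.

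This is a secondary objective. The H1a and H1b analyses do not depend on it.

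**What to change.** - State the unit of analysis for each outcome, and reconcile the general correlation and stepped-wedge statements with this paragraph.
- For survey-level outcomes, fit the models to post-go-live encounters with patient random intercepts, cluster and study-step terms, and the prior score with the time since it.
- Measure the process in the interval before the score.
- Consider a clinician random effect for clinician-level measures. Model (1) has no such term, so this is an addition and may make fitting harder.
- Report results as associations and replace the wording on which processes contribute most. Level 2 entry also depends on non-response, patient preference and clinician referral, so confounding can remain after adjusting for the prior score.
- In Specific Aim 2 Analyses, say whether the count and logit models are for count or binary clinical outcomes or for process measures, and which model applies to SPPADE scores.

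The cost is SAP wording and wider intervals. Apart from the optional clinician effect, the terms largely reuse what model (1) already contains.
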